12.3.1.3 Compliance

Based on the total daily number of sprays taken recorded by the patient on the eDiary and on the optimized dose defined at Day 15 of each treatment period and collected on the eCRF “Dose adjustment” form the compliance to study drug will be assessed, during the maintenance phase of each treatment period, by the means of the 4 below parameters:

- The compliance (%),
- The rate of “0 total daily spray (%),
- The rate of “> 12” total daily sprays (%),
- The rate of missing diary day IMP information (%),

which will be summarized by treatment arm.

Detailed calculation along with missing data handling is described in [Section 10.9](#).

Furthermore, the percentage of patients meeting study drug compliance will be presented in the following categories of days in the allowed dose range (coded as yes/no): < 80%, \geq 80% to < 90%, \geq 90% to < 100 % and = 100%.

Additionally, the **patient percentage of imputed diary days** (as defined in [Section 10.8.2](#)) which represents the percentage of days where missing morning and/or evening number of sprays taken have been imputed to ‘0’ to derive the total daily IMP dose and thus compliance is based on imputed total number of sprays taken that day will be described by treatment arm.

Optimized Dose

The optimized dose will be summarized as quantitative and categorical variable per treatment arm. The need of optimized dose adjustment will also be described along with reason for dose adjustment.

12.3.1.4 Drug Accountability

Study drug accountability including volume dispensed (mm), residual volume (mm), volume used (mm), number of sprays taken and eDiary sprays accountability (%) will be listed.

12.3.2 Prior, Concomitant and Prohibited Therapies

For any medications / non-drug therapies initiated or ongoing since Visit 1 (Screening), the start and stop date, dose, unit, frequency, route of administration, and indication will be recorded respectively in the ‘Concomitant Medication’ eCRF page and in the ‘Concomitant Physiotherapy’ eCRF page.

As nabiximols is being investigated as therapy in patients with spasticity due to MS, all patients must currently be taking at least 1 optimized oral MS antispasticity medication. Optimized oral MS antispasticity medications will include at least baclofen, tizanidine, and/or dantrolene (monotherapy or combination

therapy). Their MS antispasticity medication must have been stable for at least 30 days prior to Screening (Visit 1) and the medication is expected to remain stable throughout the duration of the trial.

All medications will be categorized by medication anatomic and therapeutic class (ATC) according to the most current version of World Health Organization-Drug Dictionary (WHO-DD) global March 2021 Dictionary Version B3 or higher according to the version in used at time of database lock.

Medication used for MS will also be categorized according to information recorded in the CRF as:

- Disease modifying drug,
- Antispasticity drug (baclofen, tizadnidine, dentrolene, benzodiazepine, muscle relaxants, botulinum toxin, gabapentin, pregabalin),
- Other MS symptoms.

Whereas physiotherapy used will be categorized according to the reason as recorded in CRF as:

- Spasticity,
- Adverse events (other than spasticity),
- Other MS symptoms,
- Other symptoms not associated with MS.

Patients should stop taking any prohibited therapy prior to Screening (Visit 1) and, within 30 days of Visit 1 regarding use of cannabis for medical or recreational purposes or any cannabinoid-based medication. These medications are prohibited for the duration of the trial.

Prohibited medications are categorized as:

- Nabiximols, cannabis or cannabinoid-based derived products,
- Botulinum toxin injections,
- Antipsychotic medications,
- Benzodiazepines (if not following protocol requirements),
- Medications that are solely metabolized by UGT1A9 (see [Appendix 7](#)),
- Medications that are solely metabolized by UGT2B7 (see [Appendix 7](#)),
- Strong CYP3A4 inducers (e.g., rifampicin, carbamazepine, phenytoin, phenobarbital, St John's Wort) (see [Appendix 8 Prohibited medications strong CYP3A4 inducers and determination criteria](#)).

In order to flag prohibited medications taken in the study, each medication taken will be compared against a pre-specified list of all prohibited medications as presented in [Appendix 7](#), [Appendix 8](#) and [Appendix 9 Other Prohibited medications and determination criteria](#).

All medications / non-drug therapies (e.g., physiotherapies) will be classified as follows:

- Prior medications are those the patient used prior to the first IMP intake. Prior medications can be discontinued before first administration or can be ongoing during the treatment periods (and wash-out period).
- Current medications are those the patient used at time of randomization and at the same time as study drug intake. This classification will mainly be used to summarize MS medications.
- Concomitant medications are any medications / non-drug therapies that are ongoing at the time of each study medication (e.g., nabiximols, placebo) intake; these medications can be initiated
 - Before first intake of study medication.
 - At the same time of study medication.

Medications concomitant the Period 1 study medication are those:

- Initiated before first intake of study medication,
- Initiated and /or taken at the same time of Period 1 study medication,
- Initiated and /or taken during the wash-out period.

Medications concomitant the Period 2 study medication are those:

- Initiated before first intake of Period 2 study medication,
- Initiated and /or taken at the same time of Period 2 study medication,

- Post treatment medications (FU medications) are any medications / non-drug therapies initiated following last IMP intake.

To classify each therapy in case of missing / partial start and /or stop date, imputation rules as described in [Section 10.14](#) will be applied.

All medications / non-drug therapies (including physiotherapies) taken during the trial will be summarized in the Safety Analysis Set. If it appears that the randomized treatment arm is different from the actual treatment arm (for summary by treatment arm) and/or if patients belonging to the Safety Analysis Set are different from those belonging to the FAS, medication summaries will be presented using both study populations.

The number and percentage of patients using each medication along with the number and percentage of patients using at least one medication within each medication group will be summarized. For each summary by treatment arm, a patient can be counted in both treatment arms for instance if:

- A patient stops one medication on or before the wash-out period and initiates a new one belonging to the same ATC class
- A patient is taking a medication concomitant to both Period 1 and Period 2.

All medications and all physiotherapy will be separately listed.

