12.3.2.4 Prohibited Medication

Prior medications: The number and percentage of patient taking prohibited prior medications will be summarized by treatment sequence and overall according to the predefined categories and standard medication name.

Concomitant medications: The number and percentage of patient taking prohibited concomitant medications will be summarized by treatment arm according to the predefined categories and standard medication name.

Tables for prohibited prior medications will be sorted by decreasing frequency of standard medication name within each predefined category based on overall incidence. In case of equal frequency, the alphabetic order will be used.

Tables for prohibited concomitant medications will be sorted by decreasing frequency of standard medication name based on the incidence within each predefined category in the nabiximols treatment arm. In case of equal frequency, based on decreasing frequency in the placebo arm then in case of equal frequency, the alphabetic order will be used.

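### SAP 12.3.2 defines concomitant medication by overlap with dosing, but its period rules use start date alone, so a medicine already stopped could also be counted under the Period 2 treatment

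*SAP*

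**What the plan says.** SAP 12.3.2 gives a general definition and then a set of period rules.

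- **Definition.** Concomitant medicines are "any medications / non-drug therapies that are ongoing at the time of each study medication (e.g., nabiximols, placebo) intake".
- **Period 1 rule.** Three alternatives: started before the first intake of study medication; started or taken alongside Period 1 study medication; or "Initiated and /or taken during the wash-out period".
- **Period 2 rule.** Two alternatives: "Initiated before first intake of Period 2 study medication", or "Initiated and /or taken at the same time of Period 2 study medication".

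The same section then explains how one patient can be counted in both arms. Its first example is: "A patient stops one medication on or before the wash-out period and initiates a new one belonging to the same ATC class". Its second is a single medicine that is concomitant with both periods.

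The classification feeds by-arm tables in SAP 12.3.2.1 to 12.3.2.5. For prohibited therapy, for instance: "The number and percentage of patient taking prohibited concomitant medications will be summarized by treatment arm according to the predefined categories". Physiotherapy follows the approach used for MS medication. Protocol 13.5.4 asks only for a summary by treatment period and gives no assignment rule.

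**The concern.** The definition turns on overlap with dosing. The first alternative in each period rule turns only on when the medicine was started. A programmer who codes the alternatives as written, joined by OR, gets different by-arm counts from one who codes the definition.

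The error would run mainly one way. Use in Period 1 carries forward into Period 2, while use that begins in Period 2 does not carry back. In a crossover this credits part of the use on one treatment to the other and blurs any difference between arms. The primary estimand (SAP Table 9.1-2) disregards prohibited medication and changes of antispasticity medication. A reader of the study report may therefore turn to these tables to see whether such use was balanced.

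The washout alternative is a separate mismatch. A medicine taken only in the washout is not ongoing at any scheduled intake, yet the Period 1 rule includes it.

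**Working it through.** The plan states no figure here to reproduce. The check applies the rules to model histories and then sizes the literal reading.

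**Inputs.** Period 1 dosing is Days 1–21, washout Days 22–30 and Period 2 dosing Days 31–51 (Protocol 9.1.2 to 9.1.4). Allocation is 1:1 (SAP 8.3).

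**Step 1: seven histories under three readings.** Each cell gives the period or periods in which the medicine counts.

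| History (start to stop day) | Period rules alone | Definition alone | Definition plus washout rule |
|---|---|---|---|
| Stopped before Day 1 (−20 to −5) | 1 and 2 | neither | neither |
| Started in screening, stopped Day 10 (−20 to 10) | 1 and 2 | 1 | 1 |
| Within Period 1 (5 to 12) | 1 and 2 | 1 | 1 |
| Washout only (23 to 28) | 1 and 2 | neither | 1 |
| Started in washout, on into Period 2 (25 to 40) | 1 and 2 | 2 | 1 and 2 |
| Ongoing throughout (−20 to 60) | 1 and 2 | 1 and 2 | 1 and 2 |
| Period 2 only (35 to 40) | 2 | 2 | 2 |

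The first four rows are counted in Period 2 only when the period rules are applied alone. Medicines ongoing throughout are classed the same way under every reading.

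**Step 2: which reading does the text support?** The second Period 2 alternative already captures any medicine taken alongside Period 2 dosing, whenever it was started. Read as a separate alternative, the first therefore adds only medicines that had stopped. The first both-arms example points the other way. A patient who stops one medicine by the washout and starts another of the same class needs the new medicine to reach the Period 2 arm only if the stopped one does not count there.

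**Step 3: size under the literal reading, with assumed use rates.**

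*Short course used only while on nabiximols, by a proportion p.* Patients randomized to nabiximols first use it in Period 1, and the literal rule counts them again in Period 2 under placebo. Patients randomized to placebo first start it in Period 2 and are not carried back.

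- Reported nabiximols rate = p; reported placebo rate = p/2.
- With p = 10%: 10% against 5%. The true difference of 10 points appears as 5.

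*Equal use q in each period, independent between periods, ignoring washout starts.* Each arm is the Period 1 treatment for half the patients and the Period 2 treatment for the other half.

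- Reported rate per arm = 0.5q + 0.5[1 − (1 − q)²].
- With q = 10%: 0.05 + 0.5 × 0.19 = 14.5% in each arm, or 1.45 times the true rate.

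Under the definition both distortions vanish: 10% against 0% in the first case, and 10% in each arm in the second.

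**The case against.** The strongest reply is that the period rules sit beneath the definition and should be read inside it: medicines that are ongoing at intake, whether begun before or during the period. Two things support this. The section's class of prior medicines already covers those discontinued before the first dose, and the both-arms example shows that stopped medicines were not meant to count in Period 2. That is good evidence of intent. It does not fully rescue the text. The washout alternative cannot be a sub-case of being ongoing at intake, so the list is not purely nested, and on the nested reading the first Period 2 alternative does no work.

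A second reply concerns the washout. A reader might infer that washout use is credited to the wrong treatment. The documents do not support that. No study medication is scheduled in the washout, and the SAP links washout findings to the Period 1 treatment elsewhere: adverse events (12.7.1), liver elevations (12.7.3.1) and unscheduled C-SSRS (12.7.5.3). The assignment is a deliberate and consistent convention. What stands is only its unstated conflict with the definition.

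A third reply is that little depends on these tables. They are descriptive. Stable background therapy counts in both arms on any reading. Several prohibited medicines, and new disease-modifying therapy or physiotherapy, are captured separately as major deviations (SAP Appendix 1, items 20 to 25), and all medications and physiotherapy are listed. This stands and limits the weight of the point.

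**Conclusion.** SAP 12.3.2 is inconsistent with itself. It requires overlap with dosing, then gives start-date-only alternatives for both periods that, coded literally, count stopped medicines under a treatment they never overlapped.

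A reader might infer that the by-arm tables will certainly be wrong. That goes too far: the definition and the both-arms example show the intent, and a careful programmer could follow them. The 10% against 5% illustration needs the literal reading, 1:1 sequences and an assumed use rate. The 14.5% figure also needs use to be independent between periods; if the same patients use the medicine in both, there is no inflation.

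The effect is confined to the descriptive by-arm medication, prohibited-therapy and physiotherapy tables. No primary or secondary efficacy estimate uses this classification. The SAP addendum, which shortens reporting after early termination, does not list medication tables, so whether they are still produced is not stated. If they are, the rule should be settled first.

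**What to change.** Replace the start-date-only alternatives with one overlap rule. A medicine or therapy is concomitant with a period if its start date is on or before the last dose date in that period, and it is either ongoing or has a stop date on or after the first dose date in that period. Apply the same rule to prohibited therapy and physiotherapy.

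If washout use is to stay with the Period 1 treatment, say so as an explicit exception to the definition and cite the matching adverse-event rule. Count a medicine started in the washout under Period 2 only if it overlaps Period 2 dosing. A separate washout row is optional.

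The cost is a few lines of SAP wording and one date derivation. Start and stop dates are already recorded (SAP 12.3.2), and SAP 10.14 already has imputation rules for partial dates.

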12.3.2.1 Non-MS Medications

Prior medications: The number and percentage of patient taking each non-MS prior medication will be summarized by treatment sequence and overall according to the first digit of the ATC class (anatomic category), first 3 digits of the ATC class (pharmacological category) and standard medication name.

Concomitant medications: The number and percentage of patient taking each non-MS concomitant medication will be summarized by treatment arm according to the first digit of the ATC class (anatomic category), first 3 digits of the ATC class (pharmacological category) and standard medication name.

Post-treatment medications: The number and percentage of patient taking each non-MS post-treatment medication will be summarized by treatment sequence according to the first digit of the ATC class (anatomic category) and first 3 digits of the ATC class (pharmacological category) and standard medication name.

Tables for non-MS prior and post-treatment medications will be sorted by decreasing frequency of anatomic class followed by pharmacological class, followed by standard medication name based on overall incidence. In case of equal frequency, the alphabetic order will be used.

Tables for non-MS concomitant medications will be sorted by decreasing frequency of anatomic class followed by pharmacological class, followed by standard medication name based on the incidence in the nabiximols treatment arm. In case of equal frequency, based on decreasing frequency in the placebo arm then in case of equal frequency the alphabetic order will be used.

12.3.2.2 Medications Used for MS

Prior medications: The number and percentage of patient taking each MS prior medication will be summarized by treatment sequence and overall according to the predefined categories and standard medication name.

Concomitant medications: The number and percentage of patient taking each MS concomitant medication will be summarized by treatment arm according to the predefined categories and standard medication name.

Post-treatment medications: The number and percentage of patient taking each MS post-treatment medication will be summarized by treatment sequence according to the predefined categories and standard medication name.

Tables for MS prior and post-MS medications will be sorted by decreasing frequency of standard medication name within each predefined category based on overall incidence. In case of equal frequency, the alphabetic order will be used.

Tables for MS concomitant medications will be sorted by decreasing frequency of standard medication name based on the incidence within each predefined category in the nabiximols treatment arm. In case of equal frequency, based on decreasing frequency in the placebo arm then in case of equal frequency the alphabetic order will be used.

12.3.2.3 Non-Antispasticity Medications and Antispasticity Medications

Prior medications: The number and percentage of patient taking either antispasticity medications or non-antispasticity medications will be separately summarized by treatment sequence and overall according to the first 2 digits of the ATC class (therapeutic category) and standard medication name.

Concomitant medications: The number and percentage of patient taking either antispasticity medications or non-antispasticity medications will be separately summarized by treatment arm according to the first 2 digits of the ATC class (therapeutic category) and standard medication name.

Post-treatment medications: The number and percentage of patient taking either antispasticity medications or non-antispasticity medications will be separately summarized by treatment sequence according to the two first digits of the ATC class (therapeutic category) and standard medication name.

Tables for prior and post-treatment antispasticity or non-antispasticity medications will be sorted by decreasing frequency in by therapeutic class, followed by standard medication name based on overall incidence. In case of equal frequency, the alphabetic order will be used.

Tables for concomitant medications antispasticity or non-antispasticity medications will be sorted by decreasing frequency of therapeutic class, followed by standard medication name based on the incidence in the nabiximols treatment arm. In case of equal frequency, based on decreasing frequency in the placebo arm then in case of equal frequency the alphabetic order will be used.

12.3.2.4 Prohibited Medication

Prior medications: The number and percentage of patient taking prohibited prior medications will be summarized by treatment sequence and overall according to the predefined categories and standard medication name.

Concomitant medications: The number and percentage of patient taking prohibited concomitant medications will be summarized by treatment arm according to the predefined categories and standard medication name.

Tables for prohibited prior medications will be sorted by decreasing frequency of standard medication name within each predefined category based on overall incidence. In case of equal frequency, the alphabetic order will be used.

Tables for prohibited concomitant medications will be sorted by decreasing frequency of standard medication name based on the incidence within each predefined category in the nabiximols treatment arm. In case of equal frequency, based on decreasing frequency in the placebo arm then in case of equal frequency, the alphabetic order will be used.

12.3.2.5 Physiotherapy

Summary of use of Physiotherapy will be summarized for each predefined category using the same approach as the one used for MS medication.

12.4 Important Protocol Deviations

All important protocol deviations (IPDs) are defined in a study specific protocol deviation guidance and classified as presented in Appendix 1 Classification of Protocol Deviations. The IPDs that are determined to affect the primary efficacy results will be classified as major IPDs as reported Appendix 1 Classification of Protocol Deviations. The occurrence of major IPDs will identify which patients maybe excluded from PP Analysis Set.

IPDs linked to COVID-19 will be identified. Patients for which at least one IPD has been identified, will be listed along with their deviation reason; demographics and treatment sequence for inclusion in the clinical study report (CSR) based on the deviation data will be entered into the clinical trial management system (CTMS).

The study team and the Sponsor will conduct ongoing reviews of the deviation data from both an internal system of record named Predictive Study Operations (PSO) and any other additional major IPDs that were missed and now identified through SAS programming of the blinded ADaM datasets, and the resulting set of evaluable patients throughout the study, adjusting the deviation criteria as seems appropriate. The PP Analysis Set must be finalized at the post-freeze data review meeting (or earlier), prior to database lock and unblinding. However, in case a patient is receiving a treatment kit he/she is not allocated to, this will be considered as a major IPD before unblinding but the impact on the PP Analysis Set will only be determined following unblinding. This particular case will clearly be identified prior to database lock.

Based on the Randomized Analysis Set, the number and percentage of patients with important protocol deviations by category, as well as the number and percentage of patient with IPDs linked to COVID-19, by category, will be summarized by treatment sequence and overall.

Based on the FAS, the number and percentage of patients with at least one major IPD and the number and percentage of patients with major IPDs linked to COVID-19 will also be summarized by treatment sequence and overall.

Using the Randomized Analysis Set and the Safety Analysis Set (if deemed necessary to account for any patients exposed out of randomization) IPDs will be listed by treatment sequence and patient identifier and flagged for belonging to FAS and Safety Analysis Set. In this listing major IPDs, and IPDs linked to COVID-19 will be identified.

Furthermore, a COVID-19 deviation listing identifying COVID-19-related IPDs will be issued including date of the deviation and duration of the impact.

